4.5 Control (usual care)

Patients randomized to the control arm will be told they meet guideline criteria for lung cancer screening, and they will be told to talk to their doctor “to see if screening is right for you.” However, control arm patients will not be shown the LCS decision aid, offered the opportunity to estimate their predicted benefits and harms of screening, or given the option of requesting a LCS screening visit via the program. Instead, control arm patients will see an animated video about exercise for lung health based on recommendations from the European Lung Foundation.⁵⁷ (**Appendix D**)

All patients will be exposed to each network’s standard LCS outreach efforts, and they will be scheduled to see a primary care provider within the next 3-4 weeks as part of the eligibility criteria – another opportunity for LCS to be addressed. As noted previously, patients in both health systems may self-refer for LCS as part of usual care.

4.6 Piloting Study Procedures

Prior to beginning enrollment of the study cohort, we will pilot these procedures on a subset of patients meeting our inclusion criteria. The purpose of this will be to ensure the automated processes function appropriately, and that accrual rates align with what is anticipated. We will create a pilot study database to validate our data queries and refine our data collection processes. However, data from participants in the pilot phase will not be included in the study analyses.

5.0 Outcome Measures

5.1 Primary Outcome

The primary outcome will be EHR-verified completion of a screening CT within 16 weeks of enrollment. While not all patients who are eligible for LCS will choose to receive it, we expect to see a significant difference in receipt of screening between arms if mPATH-Lung is effective. This will be defined as ANY chest CT within 16 weeks (and we will code to know whether it was a LDCT or some other diagnostic chest CT).

5.2 Secondary Outcomes

- 5.2.1 LCS screening decisions: LCS screening decisions will be captured by the mPATH-Lung program in the mPATH-Lung group only. (Time frame = post-intervention)
- 5.2.2 LCS clinic visits scheduled: The proportion of patients in each arm who have scheduled a LCS clinic visit will be captured by querying the EHR at each site.
- 5.2.3 LCS clinic visits completed: The proportion of patients in each arm who have completed a LCS clinic visit will be captured by querying the EHR at each site.
- 5.2.4 LCS scans ordered: The proportion of patients in each arm for whom a LCS scan was ordered will be captured by querying the EHR at each site.
- 5.2.5 LCS Clinic referral requested through mPATH
- 5.2.6 Lung RADS Results: The results of all chest CTs will be captured by querying the EHR at each site.
- 5.2.7 LCS false positives: A false positive scan will be defined as a Lung-RADS 3 or 4 result with a negative completed work-up for lung cancer or no diagnosis of lung cancer within 12 months of the scan.
- 5.2.8 Invasive procedures following LCS scan: We will query the EHR at each site to determine the number and proportion of patients in each arm who undergo an invasive procedure to investigate an abnormal LCS scan.
- 5.2.9 Complications following LCS: We will query the EHR at each site and conduct a blinded chart review to determine the number and proportion of patients in each arm who experience a complication from an invasive procedure done to investigate an abnormal LCS scan.
- 5.2.10 Number of diagnosed lung cancers (detected by screening or other) within 16 months of randomization
- 5.2.11 Whether diagnosed lung cancers were detected incidentally or related to screening
- 5.2.12 Stage of lung cancers diagnosed
- 5.2.13 Overscreening: We will determine the proportion of patients with screen diagnosed lung cancer in the mPATH-Lung and control groups who are deemed too ill for potentially curative surgery by blinded chart review.
- 5.2.14 Reach of digital outreach strategy: Reach of the digital outreach strategy is defined as the proportion of patients who complete the website study eligibility questions. The denominator includes all patients who were sent an invitation, regardless of full program completion and whether or not they were subsequently determined to be eligible for LCS.
- 5.2.15 Completion of mPATH Lung: Completion of mPATH-Lung is defined as the proportion of patients who complete mPATH-Lung to the point of indicating their screening decision. The denominator includes all patients randomized to mPATH-Lung.

We will use qualitative methods to examine situations where initial decisions and subsequent behavior are concordant as well as discordant. Our goals here are to deepen our understanding of how patients' decisions may evolve over time, and how those changes may be influenced by interactions with providers, family members, or others. We also aim to understand the facilitators and barriers to receiving LCS for those who decide they want screening. We will conduct semi-structured individual interviews with 3 groups of participants reflecting the spectrum of screening decisions and screening behavior. (**Table 3**) All interviews will be conducted after primary data collection is complete to avoid biasing outcomes.

Table 3. Groups for semi-structured interviews (n≥16 per group)

Group	Screening Decision	Screening Behavior
1	Want Screening	Half Screened / Half not Screened
2	Unsure	Half Screened / Half not Screened
3	Decline Screening	Half Screened /

Beginning 6 months after the first patient is enrolled, we will review our dataset monthly to identify participants

		Half not Screened
--	--	-------------------

randomized to the mPATH-Lung arm who have completed Aim 1 study involvement in the prior 4 weeks. A research assistant will call these patients to ask if they would be willing to participate in a 45-60-minute interview to discuss their LCS screening decision. Those completing the interview will receive a \$75 incentive. Interviews will be conducted by phone at the patient's convenience and recorded for later analysis.

Prior to completing the interview, patients will be asked a series of 7 questions to assess their LCS knowledge. (**Appendix N**) Interviews will be conducted using an interview guide (**Appendix H**). During this interview, we will first ask patients open-ended questions about their screening decision, as well as their current thinking about LCS.. We will then discuss how the patient progressed to complete screening or why they did not. A total of 12 interviews are generally considered sufficient to reach thematic saturation.^{62,63} Because half of patients in each group will have completed screening and half will have not, we anticipate we may need a larger sample to reach saturation. Therefore, we will conduct interviews with at least 16 patients in each of the 3 groups shown in **Table 3** (a minimum of 48 interviews). Each interview group will consist of an equal number of patients from each health system. We will analyze the interviews as they are conducted to assess whether saturation has been reached (i.e., no new themes emerged), and will continue recruitment if saturation is not reached.

Provider Surveys (Appendix I): Following completion of primary data collection, we will invite all primary care providers who had at least one patient randomized to mPATH-Lung to respond to a brief emailed survey that includes portions of a previously validated appropriateness instrument.⁵⁸ The survey will also collect basic provider sociodemographic and practice setting characteristics to let us examine how appropriateness varies by subgroups. We will use the Research Electronic Data Capture (REDCap) system, a web-based secure application for building and managing online surveys and databases, for this survey. Within the survey, providers will be informed of the program (purpose, key messages, procedures for lung screening referral) Providers who complete the survey will receive a \$10 digital gift card.

Provider Interviews (Appendix J): The provider survey will reveal whether providers find the mPATH-Lung digital outreach strategy appropriate. To gain a deeper understanding of why providers' hold their views about the appropriateness of mPATH-Lung, we will conduct 30-minute semi-structured interviews with a subset of at least 24 primary care providers, stratified by clinic network and chosen to reflect a diversity of views on appropriateness. Interviews will be conducted by video call, recorded for later analysis, and scheduled at a time convenient to the provider. The interview guide will explore in greater depth the items assessed on the structured survey (e.g., why or why not mPATH-Lung seems like a good match for their practice). Additionally, we will explore whether primary care providers perceive patients' ability to self-refer to the lung screening clinic for a shared decision making visit as helpful or harmful and why. Respondents will receive a \$50 digital gift card. We estimate that 12 provider interviews in each of the 2 health networks will be sufficient to achieve saturation.^{64,65} We will analyze the interviews as they are conducted, and will continue recruitment beyond 12 per health network if saturation is not reached.

6.0 Analytic Plan

6.1 Primary Analysis

The primary analysis will be carried out based on "intent to treat." All patients will be included in their randomized arm whether or not they actually finish the program. The primary objective of effectiveness will be assessed using a logistic regression model with completion of LCS (Y/N) within 16 weeks of enrollment as the outcome, treatment arm as the primary independent variable, and health system as a covariate per the design.

6.2 Secondary Analyses

In secondary analyses of effectiveness, we will assess the effects of age, sex, race and ethnicity, insurance status, and rurality on screening rates using logistic regression models. Additionally, we will conduct separate subgroup analyses for these covariates to obtain estimates and 95% confidence intervals of the intervention effect in these subgroups.

This same strategy described for analysis of completion of LCS to assess the effectiveness of the mPATH-Lung program will be used to assess the impact of the mPATH-Lung program on screening intent, scheduled and completed LCS clinic visits, test ordering, and screening-related harms (including overscreening). For LCS results, we will provide estimates with confidence intervals for the proportion of patients who have Lung-RADS 1 (normal), Lung-RADS 2 (small/stable nodule), Lung-RADS 3 (nodule with 6-month follow-up recommended), and Lung-RADS 4 (concerning nodule needing short-term follow-up or biopsy) results. Ordinal logistic or linear regression will be used to assess the effect of mPATH-Lung on patient knowledge of LCS, depending on the distribution of the outcome. We will also examine knowledge levels in those with a strong preference for or against screening.

We will use descriptive statistics to characterize participants' screening decisions, ratings on the values clarification exercise, most important attributes, and screening behavior. We will use multinomial logistic regression to examine the relationships between the most important attribute and screening decision, where the outcome is coded on three levels (want screening, unsure, do not want screening). We will include the following covariates in the model: age, sex, pack-years of smoking, knowledge score, and 5-year life expectancy (to capture comorbidity) using a previously validated model.^{66,67}

We will use descriptive statistics to characterize *Reach* and *Acceptability* by patient sociodemographic characteristics and invitation modality, and the *Appropriateness* by provider and practice characteristics. Similar to our strategy for analyzing our primary outcome, we will use logistic regression to examine the effect of patient characteristics on the *Reach* measures.

Patients will answer the acceptability survey at the end of mPATH-Lung. Each of these 7 items is scored on a 5-point scale from -2 (worst) to +2 (best), and the mean score will define *Acceptability*. Patients who fail to complete mPATH-Lung will be considered to have found the program unacceptable (score of -2). We will use multiple imputation to impute data for participants who complete mPATH-Lung but fail to complete the acceptability survey, which should be rare. Linear regression will be used to determine which patient covariates are associated with *Acceptability*. We will also examine the proportion of patients who view mPATH-Lung as acceptable (scores ≥ 0), and logistic regression will be used to determine which covariates are associated with *Acceptability*.

Each item on the provider *Appropriateness* survey is scored on a 5-point scale from -2 (worst) to +2 (best). Linear regression will be used to determine which provider and practice characteristics, including number of patients seen in the mPATH-Lung arm, are associated with *Appropriateness*. We will also estimate the proportion of providers who rate mPATH-Lung as appropriate (scores ≥ 0), and logistic regression will be used to determine which provider and practice characteristics are associated with this outcome.

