6.4 Sample Size and Power

In 2015 (the year Medicare approved payment for LCS), only 3.9% of eligible Americans were screened.⁹ Given that national screening rates are expected to increase, we will conservatively assume the screening rate in the control group will be 10%. A total sample size of 1320 patients (approximately 660 in each group) will provide 90% power for detecting a 6% absolute difference in screening rates at the 5% two-sided level of significance and approximately 80% power for detecting a 5% absolute difference in screening. Because our primary outcome measure is determined by electronic health record review and not surveys, there will be no loss to follow-up.

We anticipate sending approximately 26,000 electronic invitations to identify and accrue 1320 eligible patients. This sample size of 26,000 invitations will allow us to estimate the *Reach* of the electronic invitations to within $\pm 0.6\%$. Our sample size of 660 patients in the mPATH-Lung arm will allow us to estimate the *Reach* of mPATH-Lung (the proportion of those who complete it) to within $\pm 3.8\%$. Our sample size of 660 patients in the mPATH-Lung arm will allow us to estimate the mean *Acceptability* score to within ± 0.076 SD. Due to the highly pragmatic nature of this study, our planned sample size will stay 660, but we may over-enroll because it takes time to change the mPATH codebase once accrual targets are reached. While we are changing the codebase, participants who received invitations may continue to visit the mPATH web app and be randomized. Therefore, we acknowledge we may over-enroll by a few participants.

Following completion of primary data collection, we will invite all primary care providers who had at least one patient randomized to mPATH-Lung to respond to a brief emailed survey. We expect 466 primary care providers will have at least 1 patient in the mPATH-Lung arm (based on the binomial probability assuming 660 patients in the mPATH-Lung arm and an equal probability of seeing one of 890 health system providers). Based on our prior studies surveying providers (with response rates of 40% - 60%),^{38,70} we conservatively estimate 30% will respond which will yield approximately 140 completed surveys. Our sample size of 140 providers will allow us to estimate the mean *Appropriateness* score to within ± 0.17 SD.

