6.5 Accrual Rate

In our prior pilot study limited to patients with active portal accounts in a single health system, it required 10 weeks to identify 1000 potentially eligible patients, of whom 35% (349) completed our study program, and 10% (99) were found to be eligible for LCS, yielding 10 patients per week.¹ For this pragmatic trial, we will accrue patients from two health networks and also include patients with cellphone numbers or email addresses, significantly expanding the pool of eligible participants. Patients without portal accounts may be less likely to respond, so we conservatively estimate that we will accrue patients at half the rate (5%) of our pilot study. Therefore, we will send invitations to 260 patients per week (130 at Wake Forest and 130 at UNC) to accrue 13 patients per week, completing accrual over 2 years. We will oversample for non-white patients. We will monitor accrual rates and increase the number of invitations sent as needed.

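### Section 6.2 estimates the intervention effect separately within subgroups but plans no direct estimate of how that effect differs between them

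*Combined protocol and SAP*

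**What the plan says.** Section 6.2 (Secondary Analyses) makes two commitments on the five factors. The first is "we will assess the effects of age, sex, race and ethnicity, insurance status, and rurality on screening rates using logistic regression models". As worded, this concerns how the factors relate to being screened, not how they change the effect of mPATH-Lung. The second is "we will conduct separate subgroup analyses for these covariates to obtain estimates and 95% confidence intervals of the intervention effect in these subgroups", which gives one estimate per level and no estimate across levels.

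The next paragraph of section 6.2 carries the approach to further outcomes, beginning "This same strategy described for analysis of completion of LCS".

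The primary model in section 6.1 has "treatment arm as the primary independent variable, and health system as a covariate per the design", so it contains no interaction. Section 6.4 sizes the trial for the overall comparison only. Of 1320 patients, about 660 per arm, it says that this number "will provide 90% power for detecting a 6% absolute difference in screening rates at the 5% two-sided level of significance". It gives no power or precision for subgroups or for differences between them.

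**The concern.** Five sets of subgroup intervals raise an obvious question: does mPATH-Lung work differently by age, sex, race and ethnicity, insurance or rurality? The quantity that answers it is the difference between the level-specific effects, with its own interval. The plan does not commit to reporting it.

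Without it, readers have only the separate intervals. Each level holds part of a sample that was sized for the whole, so whether a given interval excludes no effect depends heavily on the size of the level and on chance. At stake is the interpretation of a secondary analysis. The estimate of the overall effect is not in question.

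**Working it through.** **Inputs.** From section 6.4: 660 patients per arm, control rate 10%, effects of 6 and 5 points, two-sided 5% level. Assumed, because the documents give no subgroup shares: one two-level factor split 50/50, 70/30 or 75/25, balanced between arms, with a 10% control rate in both levels.

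**1. The plan's own figures.** Power = Φ[(d − 1.96·SE₀)/SE₁], where SE₀ is the pooled and SE₁ the unpooled standard error.
- 10% vs 16%: SE₀ = √(2×0.13×0.87/660) = 0.01851; SE₁ = √((0.09+0.1344)/660) = 0.01844; power = Φ(1.286) = 0.901, against 90% stated.
- 10% vs 15%: power = 0.785, against approximately 80% stated.

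Both reproduce.

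**2. The same 6-point effect in both levels.** Applying the formula with each level's sample size per arm gives the power within each level, A and B. The chance that exactly one interval excludes no effect is A(1−B) + B(1−A).

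| Split | n per arm | Power in each level | Exactly one excludes no effect |
|---|---|---|---|
| 50/50 | 330, 330 | 0.63, 0.63 | 0.47 |
| 70/30 | 462, 198 | 0.78, 0.43 | 0.54 |
| 75/25 | 495, 165 | 0.80, 0.37 | 0.58 |

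Simulation with Wald intervals for the log odds ratio gives 0.47, 0.55 and 0.59 for the three splits. For other uniform effects it gives:
- 10% vs 15%: 0.50–0.57
- 10% vs 20%: 0.09, 0.21 and 0.29
- no effect: about 0.09

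**3. Would the direct contrast help?** Among the discordant trials at 10% vs 16%, the interaction is non-significant in about 90–94%. The help is smaller elsewhere: roughly three quarters to 90% at 10% vs 20%, and about two thirds with no effect.

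**4. Precision of the contrast.** With 10% vs 16% in both levels, the standard error of the difference in risk differences is √(0.2244/n_A + 0.2244/n_B).
- 50/50: √(2×0.2244/330) = 0.0369, so the 95% half-width is 7.2 points.
- 75/25: √(0.2244/495 + 0.2244/165) = 0.0426, so it is 8.3 points (8.4 in simulation).

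The ratio of odds ratios is known to within a factor of about 1.9–2.1 either way.

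**5. Power of the contrast.** Suppose one level goes from 10% to 16% and the other stays at 10%.
- Absolute scale, 50/50: SE = √(0.2244/330 + 0.18/330) = 0.0350; power = Φ(0.06/0.0350 − 1.96) ≈ 0.40. Across the splits it is about 30–40%.
- Odds-ratio scale: about 25–33%.

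**6. Multiplicity.** Five independent tests at 5% give 1 − 0.95⁵ = 0.226. Simulation with independent or correlated factors gives about 19–23% for at least one false positive on a given scale.

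**The case against.** The strongest reply is that the plan contains no error here. It promises estimates with intervals, no subgroup hypothesis tests and no claim of differential effect, and section 2 has no objective about effect modification. Because the levels are disjoint, a reader could derive the contrast from the published subgroup estimates. In a trial sized only for the overall effect, a purely descriptive display is defensible. All of this stands, and it keeps the point minor.

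It is also fair that the 47–59% figure describes readers who compare significance, which the plan does not do. At a uniform 10% vs 16%, the two levels' intervals overlap in about 99% of trials, including the discordant ones, so the display would seldom look like a clear difference. Overlap is not a valid test of equality, however, and it does not supply the missing estimate.

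The interaction would be imprecise. That is a reason to show its interval and not to rest conclusions on its p-value. It is not a reason to leave it out.

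One could argue that the logistic models of covariate effects leave room for interaction terms. They are not excluded, but the sentence concerns screening rates, so this is latitude and not a commitment.

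**Conclusion.** The point holds as a minor improvement: section 6.2 gives level-specific effects and plans no direct estimate of the difference between them.

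The size depends on assumptions. The 47–59% needs a two-level factor split between 50/50 and 75/25, a uniform modest effect of 10% vs 16%, and a comparison of which intervals exclude no effect. With a larger effect, or none, it is much smaller.

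A reader might infer more than the documents support:
- **That the plan will declare subgroup differences from side-by-side significance, or rules out a direct comparison.** It does neither.
- **That a uniform effect will generally look uneven about half the time.** That is not a general property of the planned output; it holds only under the conditions above.
- **That the stated intention in section 6.5, "We will oversample for non-white patients", commits the trial to comparing effects by race.** It concerns recruitment only.
- **That the primary result or sample size is weakened.** Section 6.1 is unaffected, and the power figures in section 6.4 reproduce.

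**What to change.** For each of the five factors, fit one logistic model to all randomized patients with arm, health system, factor and arm-by-factor interaction. Report the ratio of odds ratios with its 95% confidence interval, using a joint test where a factor has more than two levels. Alongside it, report the difference in absolute risk differences with its 95% interval, for example standardized from the same model, because section 6.4 powers the trial on the absolute scale. Keep the planned subgroup estimates as descriptive, and label the interaction analyses exploratory.

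The cost is a few lines of SAP text and code, with no new data and no change in sample size. The SAP should state the limits shown above: low power, an interval of about ±7 to 8 points that is wider than the planned 6-point effect, and roughly a one-in-five chance of at least one false positive across the five factors. It follows that a non-significant interaction is not evidence of a uniform effect.

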Values Clarification Exercise (Appendix C): Helping patients clarify how they balance the potential benefits and harms of screening is a critical element of shared decision making. An explicit values clarification exercise can help patients make a screening decision consistent with their values.¹⁸ Patients will complete the exercise immediately after seeing their personalized risk-benefit infographic (see Figure 2, fourth panel from left). The exercise will be adapted from previously tested values clarification instruments, including some developed by our team members.^{15,55} First,

patients will complete a rating exercise, in which they will rate the importance of the risks and benefits, or “attributes,” of the screening decision (e.g., 193 out of 1000 chance of a false positive, or 10 lives saved out of 1000) individually on a 5-point Likert scale. Attributes rated will be the same as the risks and benefits of screening covered in the video decision aid (Table 2). Afterwards, patients will complete a ranking exercise, in which they will indicate their top two attributes in order of personal importance. Finally, patients will indicate their screening preference. To maximize readability, clarity, and comprehension, we will cognitively test the values clarification exercise using “think aloud” exercises with 10-15 patients who are eligible for LCS. In this pre-test, patients will complete the values clarification exercise and a cognitive interview to help us evaluate each item’s performance (e.g., whether the content is understood in the intended manner, ease of completion) and clarity of the instructions. We will use results to iteratively improve materials between pre-testing sessions (e.g., revise wording for clarity). Patients who participate in this pre-testing phase will receive \$50 for their time and will be ineligible for the larger study.

Electronic Summaries: On completion of mPATH-Lung, participants will be given the option to download a program summary including their personalized risk-benefit infographic, values clarification results, and screening decision.

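### Screening harms are compared with the primary logistic model and no sparse-event method, so the odds ratio is likely to have no finite estimate for complications, may have none for procedures, and is least workable for overscreening

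*Combined protocol and SAP*

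**What the plan says.** Section 6.1 defines the primary strategy. Effectiveness is "assessed using a logistic regression model with completion of LCS (Y/N) within 16 weeks of enrollment as the outcome", with treatment arm as the main independent variable and health system as a covariate, by intention to treat.

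Section 6.2 applies the same strategy to secondary outcomes, including "scheduled and completed LCS clinic visits, test ordering, and screening-related harms (including overscreening". Neither section names an exact or penalised method, a risk difference, or a rule for an arm with no events. Neither gives expected harm counts.

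The harms are defined in section 5.2:
- False positives (5.2.7) are Lung-RADS 3 or 4 scans that do not lead to a cancer diagnosis.
- Invasive procedures (5.2.8) are those done to investigate an abnormal screening scan.
- Complications (5.2.9) concern patients who "experience a complication from an invasive procedure done to investigate an abnormal LCS scan".
- Overscreening (5.2.13) is a proportion among patients with screen-diagnosed lung cancer.

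For 5.2.8 and 5.2.9, numbers and proportions per arm are promised. Section 6.4 gives power for the screening comparison only.

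**The concern.** The harms are nested. A procedure needs an abnormal scan, and a complication needs a procedure, so each step leaves fewer patients with an event. The primary model suits an outcome expected in 10% to 16% of patients. It does not suit one expected in a fraction of a per cent. If an arm has no events, the likelihood has no finite maximum for the arm effect, and a Wald interval around it is meaningless.

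At stake is the between-arm comparison of harm. More screening is the intended effect, so some excess harm in the mPATH-Lung arm is expected, and the useful question is how large it is in absolute terms. If the pre-specified comparison fails, its replacement will be chosen after the counts are known. If it runs on few events, the odds ratio will be too imprecise to say much about the size of the excess.

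**Working it through.** **Inputs from the plan (section 6.4).** "A total sample size of 1320 patients (approximately 660 in each group) will provide 90% power for detecting a 6% absolute difference" and "at the 5% two-sided level of significance and approximately 80% power for detecting a 5% absolute difference in screening". The control screening rate is 10%, so the mPATH-Lung rate is 16% under the 6-point difference.

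**Reproducing the plan's power.** A two-proportion calculation with 660 per arm and two-sided 5% gives 90.1% for 10% v 16% and 78.5% for 10% v 15%. Both agree with the stated 90% and approximately 80%.

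**Patients scanned within 16 weeks.** 660 × 0.10 = 66 in control; 660 × 0.16 = 105.6 with mPATH-Lung.

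**Chance of an arm with no events.** Let r be the event rate per scanned patient. No procedure or complication rate is given, so every r below is an assumption.
- Control arm empty: a = (1 − 0.10r)^660
- mPATH-Lung arm empty: b = (1 − 0.16r)^660
- At least one arm empty: 1 − (1 − a)(1 − b)

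| Assumed r | Expected events, control v mPATH-Lung | a | b | At least one arm empty |
|---|---|---|---|---|
| 0.2% | 0.13 v 0.21 | 0.876 | 0.810 | 98% |
| 0.5% | 0.33 v 0.53 | 0.719 | 0.590 | 88% |
| 1% | 0.66 v 1.06 | 0.517 | 0.348 | 68% |
| 2% | 1.32 v 2.11 | 0.267 | 0.121 | 36% |
| 3% | 1.98 v 3.17 | 0.138 | 0.042 | 17% |
| 5% | 3.30 v 5.28 | 0.037 | 0.005 | 4% |

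For complications, assumed rates of 0.2% to 1% give 98% to 68%. For procedures, assumed rates of 1% to 5% give 68% down to 4%.

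**Overscreening.** At an assumed yield of 1% to 3% screen-diagnosed cancers per scan, the denominator is 66 × 0.01 to 66 × 0.03 = 0.7 to 2.0 control patients, and 105.6 × 0.01 to 105.6 × 0.03 = 1.1 to 3.2 mPATH-Lung patients. A finite arm effect needs at least one patient with and one without the outcome in each arm, hence at least two cancers per arm. With m = 0.10 × yield, the chance that control has fewer than two is (1 − m)^660 + 660m(1 − m)^659. This is 86% at 1% yield and 41% at 3%, before asking how those patients divide.

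**False positives.** The only per-patient figure is an illustrative item in the values clarification exercise (section 4.4): "193 out of 1000 chance of a false positive, or 10 lives saved out of 1000".
- Expected patients: 66 × 0.193 = 12.7 v 105.6 × 0.193 = 20.4
- Risks among all randomised: 1.93% v 3.09%; difference 1.16 points
- Standard error: √[(0.0193 × 0.9807 + 0.0309 × 0.9691)/660] = 0.86 points
- 95% CI: 1.16 ± 1.96 × 0.86, or about −0.5 to 2.8 points

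The model can be fitted here, but the comparison is imprecise.

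**The case against.** Several stronger readings are tempting, and the documents do not support them.

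**That the model will usually fail for procedures as well as complications.** This depends on rates the documents do not give. At 3% to 5% per scan, an empty arm has a 17% to 4% chance, which is not often. The table also uses 16-week uptake. Outcomes 5.2.7 to 5.2.9 carry no 16-week limit on scans, and the timeline in section 6.6 runs harm surveillance into Year 5. Later scans would raise counts and lower these probabilities. This stands, so procedures are treated here separately and conditionally.

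**That low power for false positives is a defect.** At 193/1000 the same two-proportion calculation gives 27% power. The range is 16% at an assumed 10% per scan to 49% at 39%, a figure that section 1.0 quotes over three screening rounds. The plan claims no power for this secondary outcome, the 193/1000 is not a design assumption, and no change of model would add information. This stands.

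**That the plan leaves readers without absolute harms.** Per-arm numbers and proportions are promised for procedures and complications, and section 6.2 gives estimates with confidence intervals for Lung-RADS categories. What is missing is an interval for the between-arm difference, and explicit per-arm counts for false positives.

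**That the sponsor intends to treat non-significance as safety.** No passage says so. It is a risk of misreading.

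The plan also does not specify Wald intervals. With one empty arm, a likelihood-ratio test and a one-sided profile-likelihood bound remain available within ordinary logistic regression. That softens the problem but does not supply a finite estimate, and the plan does not call for either.

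**Conclusion.** The concern holds in a limited form. The stated comparison for harms is poorly matched to the number of events the design can produce. It is likely to have no finite odds ratio for complications, with a chance of 68% or more at any assumed rate up to 1% per scan. For procedures it may have none: 36% at an assumed 2%, falling to 4% at 5%. Overscreening is where the model is least workable, with about one to three patients per arm at an assumed yield of 1% to 3%. False positives can be analysed, with an expected interval of about −0.5 to 2.8 points around a 1.2-point difference at the illustrative rate.

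These figures rest on 660 per arm, 10% v 16% uptake, scans within 16 weeks, and the assumed rates shown. The 193/1000 may also not match the Lung-RADS definition in 5.2.7. The primary analysis is unaffected. The change should still be made, because a better-suited method is available at little cost and ought to be fixed before the counts are seen.

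**What to change.** In section 6.2, take the harms out of the sentence that applies the primary strategy, and specify the following:
- For 5.2.7 to 5.2.9, report the number and proportion per arm among all randomised patients. Make the between-arm comparison a risk difference stratified by health system, with a score-type or exact 95% confidence interval.
- If an odds ratio is also wanted, use Firth or exact logistic regression.
- For 5.2.13, report per-arm counts of screen-diagnosed cancers and of those judged too ill for surgery, without a model.
- State that a non-significant harm comparison will not be read as absence of harm.

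The cost is minor SAP wording and programming, with no new data. The estimates will look less definitive than an odds ratio with a p-value, and the false-positive interval may still include zero.
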